## **5.2 Study Drug Management**

Study drug will be managed by staff at the University Neuropsychiatric Institute. Subjects will be issued a subject ID number. This number will be used to randomize subjects into High ISO/BS+ or Low ISO/BS- arms of the study. Randomization will be conducted by a designated un-blinded member of the study team. Emergency un-blinding information will be maintained by a designated custodian. Subjects' un-blinding information will only be accessed by the study team in case of a medical emergency. If a drug disclosure is made, a record must be made by the Investigator detailing the purpose, date, and personnel involved.

## **5.3 Clinical Assessments**

**5.3.1 Primary Response Assessments:** The primary outcome measure is change in depressive symptoms assessed by the Hamilton Rating Scale for Depression (HRSD-24), which is the most widely used method of evaluating the effectiveness of treatments to relieve depression. HRSD-24 will be administered as part of a clinical interview by blinded investigators prior to beginning the treatments, then repeated before treatment #6 and at the end of treatments.

**5.3.2 Secondary Response Assessments to be acquired before each treatment:** Also as standard of care for patients receiving ECT, the participant will fill out the Quick Inventory of Depressive Symptomatology (QIDS-SR) which is a patient self-report measure of depressive symptoms prior to each treatment session. QIDS scores will also be used as a safety measure. If 2 consecutive QIDS scores indicate worsening of depressive symptoms, below pre-treatment values, the study participant will meet with one of the study Psychiatrists to discuss treatment alternatives. The Montreal Cognitive Assessment (MoCA), Generalized Anxiety Disorder scale (GAD-7), and Work and Social Adjustment Scale (WSAS) will be administered prior to beginning the treatments, then repeated before treatment #6, and 48-72 hours post treatment #10.

**5.3.3 Follow-up Assessments to be acquired monthly for up to 6-months post treatment period:** Follow-up assessments will include QIDS-SR, WSAS, and an opened ended question about the participant's experience during the study. Follow-up assessments will be administered over the phone or by email with a link to an electronic survey housed on REDCap (a secure online database). A voicemail may be left (with prior permission) regarding the follow-up assessments.

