## 2. Study Objectives

### 2.1 Study 1

Study 1 will test the central hypothesis that high dose isoflurane anesthesia inducing EEG burst suppression (High ISO/BS+) is a more effective intervention for severe depression when compared to a low dose isoflurane anesthesia that does not induce EEG burst suppression (Low ISO/BS-). The proposed study is a randomized, double-blind trial that will evaluate 30 actively depressed participants with moderate to severe depression. Depression outcomes will be compared between two groups of participants (n=15 per group) who have received 10 treatment applications over a period of three weeks of either High ISO/BS+ or Low ISO/BS-.

Aim 1. To determine whether High ISO/BS+ is more effective than Low ISO/BS- in producing either a treatment response (defined as 50% reduction in depression scores) or full remission of depressive symptoms. We hypothesize that significantly more depressed participants randomized to receive 10 treatments of High ISO/BS+ compared to Low ISO/BS- will show a positive treatment response or full remission by treatment end. Based on the STAR\*D Trial, a responder is a participant showing 50% reduction in depression score and full remission is defined as a score of 0-10 on the HRSD-24 scale and score of 0-5 on the QIDS-SR16.

Aim 2. Preliminary data on neural and immune pathways that are differentially affected by the 2 treatments and associated with antidepressant effects will be explored by comparing changes from pre-treatment to post-treatment in full transcriptome leukocyte gene expression (using the RNA Seq method).

Aim 3. To measure the central neurochemical effects of isoflurane treatment, we will quantify neurotransmitter levels (GABA and glutamate) using magnetic resonance spectroscopy.

### 2.2 Pilot Study 2

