## **7. Statistical Considerations**

Statistical analyses will employ a statistical mediation model framework. Any participant missing necessary information will be excluded from statistical analysis. Only participants with usable data will be included in the analyses. If the original statistical plan becomes infeasible, the original plan and the modifications made will be reported.

**7.1 Aim 1.** To determine if significantly more depressed participants randomized to receive 10 treatments of High ISO/BS+ will show a positive treatment response (defined as 50% reduction in depression scores) or achieve full remission of symptoms by treatment end compared to those in the Low ISO/BS-group, odds of treatment response and remission will be compared between groups using logistic regression analysis with positive response at treatment end (yes/no) as the dependent variable, and treatment group (High ISO/BS+ vs Low ISO/BS-) as the independent variable. Positive treatment response is defined as 50% reduction in depression scores, and remission will be defined as a score of 0-10 on the HRSD-24 scale.

Covariates will include baseline depression severity and possibly other baseline demographic and clinical measures as needed.

**7.2 Aims 2 and 5.** Using RNA SEQ methods, we will also explore whether participants who respond to treatment show blood-based changes in gene expression of neural and immune pathways previously associated with refractory depression or suicidality by our group or others. A t-test or non-parametric Wilcoxon test will be used, as appropriate. Change from baseline to end of treatment in gene expression levels will be correlated with change from baseline to end of treatment in HRSD-24.

**7.3 Aim 4.** In the open-label trial of propofol, initial evidence of efficacy will be defined by the percent of participants who show at least a 20% reduction in both HRSD and QIDS scores (initial improvement, as employed in the STAR D investigation) and who are propofol/BS+ responders (defined as 50% or more reduction in both HRSD-24 and QIDS scores). Secondary evidence of efficacy will be defined by comparing the percent of participants who are responders to propofol/BS+ vs. to the Low ISO/BS- control condition in the randomized trial.

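### Section 5.3.1 makes change in HRSD-24 primary, but 7.1, the only High vs Low ISO efficacy test, compares response and remission without ranking them, and remission is defined differently in Aim 1 and 7.1

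*Combined protocol and SAP*

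**What the plan says.** **Primary outcome.** Section 5.3.1 states: "The primary outcome measure is change in depressive symptoms assessed by the Hamilton Rating Scale for Depression (HRSD-24"). The scale is given at baseline, before treatment 6 and at the end of treatment. No summary measure is named.

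**Objective.** Aim 1 (Section 2.1) asks whether High ISO/BS+ is better at "producing either a treatment response (defined as 50% reduction in depression scores) or full remission of depressive symptoms". It defines full remission as HRSD-24 0-10 together with QIDS-SR 0-5.

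**Analysis.** Section 7.1 says "odds of treatment response and remission will be compared between groups using logistic regression analysis with positive response at treatment end (yes/no"). Response is thus the only outcome variable it names for the model. Further on, it defines the two endpoints: "Positive treatment response is defined as 50% reduction in depression scores, and remission will be defined as a score of 0-10 on the HRSD-24". On the model: "Covariates will include baseline depression severity and possibly other baseline demographic and clinical measures as needed".

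**Elsewhere in Section 7.** HRSD-24 change as a score appears only in 7.2: "Change from baseline to end of treatment in gene expression levels will be correlated with change from baseline to end of treatment in HRSD-24". Section 7.3 defines propofol responders on two scales, "defined as 50% or more reduction in both HRSD-24 and QIDS scores", and then plans "comparing the percent of participants who are responders to propofol/BS+ vs. to the Low ISO/BS- control condition in the randomized trial".

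**Timing.** The Schedule of Activities and Sections 5.3 and 6.3 place the last HRSD-24 after treatment 10. QIDS is completed before each treatment, so the last one precedes treatment 10. The next is at monthly follow-up.

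**The concern.** Someone analysing Study 1 from this text has several choices to make after the data are in: change score or yes/no endpoint, response or remission, and which of two remission rules. Aim 1's wording can mean a composite for each participant or success on either of two tests. The plan settles none of these. Study 1 is presented as the rigorous randomised test of the burst suppression hypothesis, with a directional claim of significantly more responders or remitters. With 15 per arm, a single participant counted differently can move the result across the significance line. A reader of the final report could not tell whether the reported endpoint was the one intended beforehand.

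**Working it through.** **1. Is there a plan figure to reproduce?** No. Section 4.5 justifies up to 15 per arm by the earlier study of 8 participants. It gives no alpha, power, control rate, effect size or SD. Everything below assumes a two-sided 0.05 level and 15 per arm.

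**2. The definitions side by side**

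| | Aim 1 (2.1) | 7.1 | 7.3 |
|---|---|---|---|
| Response | 50% reduction, scale not named | 50% reduction, scale not named | 50% or more on HRSD-24 and QIDS |
| Remission | HRSD-24 0-10 and QIDS-SR 0-5 | HRSD-24 0-10 | not used |

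The Aim 1 remitters are a subset of the 7.1 remitters, so the 7.1 rate is equal or higher. The rules differ only for participants with HRSD-24 0-10 and QIDS above 5.

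**3. Why the choice of endpoint matters.** Section 3 reports 75% response and 50% remission on High ISO. Normal approximation for two proportions, with p̄ the mean of the two rates:

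power = Φ{[(p1 − p2) − 1.96·√(2p̄(1−p̄)/15)] / √([p1(1−p1) + p2(1−p2)]/15)}

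- Response 75% vs an assumed 25%: (0.50 − 1.96×0.1826)/0.1581 = 0.90, power 0.82. Vs an assumed 40%: 0.49.
- Remission 50% vs an assumed 25%: (0.25 − 1.96×0.1768)/0.1708 = −0.56, power 0.29. Vs an assumed 10%: 0.68.

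**4. One reclassified participant under the planned logistic model (arm only).** Suppose 11 vs 5 remit under 7.1, and one of the 11 has QIDS above 5, giving 10 vs 5 under Aim 1.

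- Likelihood ratio: G = 2[ℓ(a/15) + ℓ(b/15) − ℓ((a+b)/30)], where ℓ is the binomial log-likelihood at the observed proportion. For 11 vs 5, G = 4.96, p = 0.026. For 10 vs 5, G = 3.40, p = 0.065.
- Wald, 11 vs 5: ln[(11×10)/(4×5)] = 1.705, SE = √(1/11 + 1/4 + 1/5 + 1/10) = 0.801, z = 2.13, p = 0.033.
- Wald, 10 vs 5: ln[(10×10)/(5×5)] = 1.386, SE = √(1/10 + 1/5 + 1/5 + 1/10) = 0.775, z = 1.79, p = 0.074.

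These counts show the mechanism; they are not a forecast (11/15 = 73%, above the 50% remission in Section 3).

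**5. How often the two remission rules disagree.** Simulation, 40,000 trials per scenario. Assumed: percent reduction on the two scales is bivariate normal with equal means, SD 30 points and correlation 0.6-0.8. The mean is set so that the chance of a 50% reduction equals the response rate. HRSD-24 baseline has mean 30, SD 6, minimum 19; QIDS has mean 17, SD 3, minimum 11. Both scales are treated as measured at the same time. High ISO response is 75%.

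| Low ISO response | Opposite verdicts, likelihood ratio | Opposite verdicts, Fisher |
|---|---|---|
| 25% | 19.0-21.6% | 23.8-27.2% |
| 35% | 23.0-26.2% | 22.4-25.8% |
| 40% | 23.2-26.5% | 19.9-23.3% |

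A repeat simulation gave 19-28%. Power under the two rules differed by only about 0-4 points, with no consistent sign. Among HRSD-24 remitters, 22-29% fail QIDS 0-5 when response is 75%, and 44-57% when it is 35%.

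**6. Response or remission in Aim 1**

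- *As a composite on HRSD-24.* Entry requires a score above 18. Among whole-number scores, the only remission that is not also a response is 19 falling to 10: (19 − 10)/19 = 47.4%. The composite is practically the response endpoint and has no real multiplicity cost.
- *As a win on either test.* Exact enumeration with no true effect, response 30-75% and remission 15-50%: type I error 8.3-11.7% by likelihood ratio (response alone 4.6-6.0%), but 2.7-3.2% by Fisher (1.6-1.8%).

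**The case against.** The best defence is that the plan is loosely drafted rather than empty. Section 5.3.1 names an instrument and a construct, and a 50% reduction is a yes/no form of change from baseline. Section 7.1 names one dependent variable, response, which can be read as giving it the lead. The scale can be inferred, because HRSD-24 is listed as primary, QIDS as secondary, and the earlier study defined response on HRSD. Section 6.3 also calls the study a pilot. Much of this stands: the primary outcome does have an indirect analysis. But the reader has to infer it, 7.1 also says remission will be compared, and no inference reconciles two different written rules for remission.

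Four stronger readings are tempting and are not supported:

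- *The plan inflates type I error.* That depends on reading Aim 1 as a win on either endpoint and on the test used. With Fisher the rate stays near 3%.
- *One remission rule favours a positive result.* The rules often disagree, but neither systematically helps High ISO.
- *A participant could remit under Aim 1 and not under 7.1.* This is impossible, since Aim 1 adds a condition.
- *Section 7.3 counts propofol and Low ISO by different rules.* The natural reading is that the definition just given there applies to both groups. It should be said, but it is not a demonstrated bias.

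**Conclusion.** The point holds on the text. The declared primary outcome has no matching High vs Low ISO analysis as a score. The analysis that is planned covers two endpoints and does not say which carries the conclusion. Aim 1 and 7.1 contradict each other on remission, and Aim 1's rule has no visit at which both scales are taken. None of this rests on simulation.

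The size does rest on assumptions. With the inputs in step 5, none of which the documents supply except the 75% High ISO response and 15 per arm, the choice of remission rule alone reverses the verdict in about 19-28% of trials. The time gap between the last QIDS and the last HRSD-24 is not modelled. The change should be made: it is small, and it decides what the trial can claim.

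**What to change.** Amend the wording of 2.1, 5.3.1, 7.1 and 7.3:

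- In 5.3.1, Aim 1 and 7.1, name one primary endpoint: response on HRSD-24, a reduction of 50% or more from baseline at treatment end. Test it with the planned logistic regression, adjusted for baseline HRSD-24.
- Make remission secondary and define it as HRSD-24 0-10 in both Aim 1 and 7.1. Reword Aim 1 to show this order.
- Keep HRSD-24 0-10 plus QIDS 0-5 as a sensitivity analysis, and state that it uses the QIDS completed before treatment 10.
- Report an ANCOVA of end-of-treatment HRSD-24 on arm and baseline HRSD-24 as a supportive analysis of the change named in 5.3.1.
- In 7.3, state that its responder rule applies to both propofol and Low ISO participants.

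Firth penalisation, testing remission only after a significant response, and removing the optional covariates are reasonable refinements, but the contradiction does not require them.

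**Cost.** No new visits or assessments. One endpoint carries the headline claim, so the chance of a positive result is somewhat lower than if either endpoint could win. Simulations with a penalised, baseline-adjusted version of the model put the loss at about 4-13 percentage points.

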| QIDS, WSAS, Study XP  |           |          |        |   |   |   |        |   |   |        |   |    |         | X                                 |

 Study 1 only

 High ISO/BS+, Low ISO/BS-, or propofol

 Time to eye opening, time to sitting without dizziness, and time to ambulation and ingestion of liquids without vomiting. Occurrence rates of nausea and vomiting, presence of EKG abnormalities and somatic complaints, and total time for each will also be recorded. Orientation time will be assessed as the earliest time post-treatment at which a participant is able to recall 4 of 5 orientation items (name, date of birth, age, place, day of the week).

 An opened ended question about the participant's experience during the study

 Follow-up measures will take place monthly after the end of treatment series and will continue for 6 months.

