### **4.1 Inclusion Criteria**

We will recruit depressed patients referred to the University Neuropsychiatric Institute for an ECT consult.

- Diagnosis of Major Depressive Disorder (MDD) or bipolar Disorder (I or II, most recent episode must be depression)
- Failed at least 2 anti-depressant treatments and no ECT in past 6 months
- Age between 18-55 years
- BMI < 40
- Hamilton Rating Scale for Depression (HSRD) score > 18
- Quick Inventory of Depression Scale (QIDS) score > 10.

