### **6.3 Safety and Efficacy Monitoring**

All serious adverse events will be reported within 5 days to the Data and Safety Monitoring Board (DSMB) and IRB by the Principal Investigator or study coordinators. These would include life-threatening cardiac arrhythmias, respiratory arrest, myocardial infarction, stroke, and death. Moderate adverse events including worsening of depressive symptoms will be reported to the DSMB. An interim data analysis will be performed at the midpoint of this pilot investigation, after data is obtained from 5 participants in each of the treatment conditions. The study will be terminated if significantly greater negative outcomes are associated with either isoflurane treatment or propofol treatment.

Prior to each treatment, participants will fill out the QIDS-SR. HRSD-24 will be obtained at baseline, before treatment 6, and after treatment 10. All participants will be assessed before the 6th treatment. If participants in Low ISO/BS- or propofol treatment groups show clinical deterioration (defined by 2 consecutive QIDS scores below baseline OR a decrease in HRSD-24 before the 6th treatment), they will be offered treatment at the 80% burst suppression level (High ISO/BS+) as it has proven effective in reducing depression or ECT as the standard of care treatment. Participants in High ISO/BS+ treatment who show clinical deterioration, as defined above, will be offered ECT. All serious adverse events will be reported within 5 days to the DSMB by the Principal Investigator or study coordinators. The DSMB will also be notified within 10 business days if a study participant is showing signs of clinical deterioration (defined as 2 consecutive QIDS scores below baseline OR HRSD-24 below baseline). Progress reports will be submitted every 6 months. If a participant has a serious reaction to anesthesia, they will be withdrawn from the study.

As exploratory biomarkers, we will evaluate whether quantitative cortical EEG changes early in treatment (obtained from dual lead BIS data in each treatment session) are associated with subsequent remission in depressive symptoms.

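### The deterioration rules in 5.3.2 and 6.3 are worded in reverse, and the monthly follow-up QIDS-SR has no score-based route to a clinician

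*Combined protocol and SAP*

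**What the plan says.** **Rules for worsening.**

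- Section 5.3.2, for scores taken before each treatment: "If 2 consecutive QIDS scores indicate worsening of depressive symptoms, below pre-treatment values, the study participant will meet with one of the study Psychiatrists".
- Section 6.3, for the offer of rescue treatment: deterioration is "defined by 2 consecutive QIDS scores below baseline OR a decrease in HRSD-24 before the" sixth treatment. Low-dose isoflurane and propofol participants are then offered High ISO/BS+ or ECT. High ISO/BS+ participants are offered ECT.
- Section 6.3, for the monitoring board: "The DSMB will also be notified within 10 business days if a study participant is showing signs of clinical deterioration", with deterioration "defined as 2 consecutive QIDS scores below baseline OR HRSD-24 below baseline".

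**Direction of the scales.** Section 4.1 requires "Quick Inventory of Depression Scale (QIDS) score > 10" and an HRSD score above 18. Section 2.1 (Aim 1) puts remission at 0-10 on the HRSD-24 and 0-5 on the QIDS-SR, and defines response as a 50% reduction.

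**Follow-up.** Footnote 5 to the Schedule of Activities states: "Follow-up measures will take place monthly after the end of treatment series and will continue for 6 months". Section 5.3.3 lists QIDS-SR, WSAS and one open question, and adds: "Follow-up assessments will be administered over the phone or by email with a link to an electronic survey housed on REDCap". The HRSD-24 is not part of follow-up: "HRSD-24 will be obtained at baseline, before treatment 6, and after treatment 10".

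**General commitments.** Section 6.3 has worsening depression reported to the DSMB as a moderate adverse event. Section 9.1 (Risks of Worsening Depression) undertakes to discuss other treatments if symptoms get worse. Neither is limited to the treatment weeks.

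**The concern.** A safety threshold has to point the right way before it can be carried out by site staff or programmed as an alert. Here the operative words in 6.3 describe a participant who is getting better. The action attached to them is a change of treatment, to ECT or High ISO/BS+. Applied literally before treatment 6, they would offer a switch to improving participants and none to a participant whose score has risen. That would be unsafe, and it would also disturb the comparison in Aim 1.

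The follow-up gap matters because relapse is foreseeable. Participants have failed at least two antidepressant treatments and are mostly recruited through ECT consultations. In the group's earlier open-label study (Section 3), gains held for four weeks in most, not all, of those given high-dose isoflurane. This trial follows people for six months. A survey completed from an emailed link can sit unread unless the protocol says who looks at it and what that person does.

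**Working it through.** No sample-size or error-rate figure is involved, so the check compares the texts and then uses simple arithmetic.

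**1. Which way the rules point.** Let *b* be the pre-treatment QIDS and *s* a later score. As written, a score is flagged when *s* < *b*. Entry gives *b* ≥ 11, assuming the QIDS before treatment 1 is still in the entry range. Checking every pair with *b* from 11 to 27 and *s* from 0 to 27 (27 is an assumed upper limit that does not affect the result):

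| Later score | Flagged by the written rule? |
|---|---|
| Remission, *s* ≤ 5 | Always, since 5 < 11 |
| Response, *s* ≤ *b*/2 | Always |
| Worse than baseline, *s* > *b* | Never |

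The same holds for the HRSD-24 limbs. Entry is above 18 and remission is 0-10, so a fall is improvement. Section 5.3.2 contradicts itself (worsening, but *below*). The two definitions in 6.3 are reversed outright.

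**2. What a follow-up QIDS-SR score can set off.**

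| Provision | Applies in follow-up? | Reaches a clinician? |
|---|---|---|
| 5.3.2 psychiatrist meeting | Not stated; its heading ties it to scores before each treatment | Yes, if it applied |
| 6.3 rescue offer | No; tied to the treatment course | Yes |
| 6.3 DSMB notice, QIDS limb | Yes; no phase limit, two scores needed | No, DSMB only |
| 6.3 DSMB notice, HRSD-24 limb | No; last taken after treatment 10 | No |
| 6.3 moderate adverse events | Yes; one sign is enough | No, DSMB only |
| 9.1 discussion of options | Yes, in general terms | Yes, but no process for remote scores |

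Scheduled monitoring (Section 6) is six-monthly after the first two completers, an interval as long as the whole follow-up.

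**3. Timing of the DSMB notice once its direction is corrected.** Monthly scores are 365.25/12 = 30.4 days apart. If worsening starts between two follow-up scores and persists, the second flagged score comes between 30.4 days and 2 × 30.4 = 60.9 days after onset. Taking 10 business days as 14 calendar days from that score, the notice may be as late as 30.4 + 14 = 44.4 to 60.9 + 14 = 74.9 days after onset. A first bad score at month 6 has no later scheduled score to confirm it. These times concern the DSMB notice only.

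**4. Which single-score trigger works in follow-up.** Take (a) at or above the pre-treatment baseline, or (b) above 10 in a participant whose last treatment-phase score was 10 or below.

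| Baseline → end of treatment → follow-up | Strictly above baseline | (a) | (b) |
|---|---|---|---|
| 11 → 5 → 11 | No | Yes | Yes |
| 20 → 5 → 11 | No | No | Yes |
| 24 → 12 → 24 | No | Yes | Does not apply |
| 24 → 12 → 23 | No | No | Does not apply |

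The scores are illustrative. A trigger strictly above baseline misses every row. Row 3 is a 50% responder (24 − 12 = 12) who relapses fully; only *at or above* catches this. Any 50% responder ending at 11 or more (baseline 2 × 11 = 22 or more) is in that position. Row 4 stays uncaught.

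**5. Workload.** 6 monthly scores × (15 + 15 + 10) participants = 6 × 40 = 240 at most. Section 4.3 also gives a total of 45, which would make it 6 × 45 = 270.

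**The case against.** The intent is not in doubt. Section 6.3 labels its definitions clinical deterioration and 5.3.2 speaks of worsening, so experienced clinicians are unlikely to act on an improving score. This stands as far as practice goes. A reader might infer that improving participants will be sent to ECT and worsening ones left alone; the documents do not support that. It does not excuse the wording, because the written definition is what governs the offer and the notice.

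A reader might also infer that nothing in the protocol covers worsening after treatment. That is too strong. The adverse-event sentence in 6.3 and the undertaking in 9.1 have no phase limit, need no second score and point the right way. What they lack is a cut-off, a reviewer or a time limit for a score that arrives remotely.

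The treatment-only reading of 5.3.2 rests largely on a heading. The same paragraph covers scales taken at only three time points, and it describes QIDS as a safety measure without restriction. Treatment-only is the likelier reading, not the only one. For that reason the wider spacing of follow-up scores should not be presented as a delay in psychiatrist contact: the plan does not state that a two-score psychiatrist rule runs in follow-up.

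Finally, Section 8 (Training and Resources) and the consent form were not available for this point, so a staff procedure there cannot be excluded. Some participants will have their own psychiatrist, and phone follow-up puts staff in direct contact with them.

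**Conclusion.** The direction error is definite. As written, the two definitions in 6.3 flag every remission score and every 50% response, and no score above baseline; 5.3.2 is internally inconsistent. This rests only on the entry and remission thresholds in the protocol.

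The follow-up gap is real but secondary. The monthly QIDS-SR has no stated score-based path to a clinician, and the one QIDS rule that reaches into follow-up is a slow notice to the DSMB. The documents give no relapse rate, so the number of participants who might be missed cannot be estimated, and no delay in psychiatrist contact is claimed. Both parts should be corrected. The first matters more because it governs decisions during treatment.

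**What to change.** 1. **Direction.** In 5.3.2 and in both 6.3 definitions, change *below* to *above*. In the rescue definition, replace the decrease in HRSD-24 with an increase in HRSD-24 from baseline.
2. **Follow-up.** In 5.3.3, state that every follow-up QIDS-SR, by phone or survey, goes to a study psychiatrist through a REDCap alert that does not show the treatment arm. Require prompt contact, within a time limit for the team to set, after one score that is (a) at or above the pre-treatment baseline (QIDS before treatment 1), or (b) above 10 in a participant whose last treatment-phase QIDS (before treatment 10) was 10 or below.

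**Cost.** A protocol amendment and an alert; no extra visits and no unblinding. The follow-up change cannot affect the primary endpoint, which is measured before follow-up starts. The price is clinician time for at most 240 scores and some contacts for rises that settle. Condition (b) fires on a one-point move from 10 to 11, and condition (a) fires for a participant who never improved from baseline. A participant who ends treatment above 10 and worsens without reaching baseline meets neither condition and is left to the psychiatrist's judgement on reading the score. Treatment started after a contact will alter later follow-up scores, so its date should be recorded.
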